### *Secondary analyses for Aim 2*

1) determining if PTDM is predicted by pre- or post-transplant levels of IL-33/sST2 from serum/tissue microdialysate, or by the frequency of circulating ST2+Th1 cells and ST2+Tregs, 2) analyzing whether IL-33/sST2 levels and ST2+Th1 cells and ST2+Tregs correlate with insulin/glucagon secretion during OGTT and hyperglycemic clamps, 3) test whether *in vitro* exposure of HCT recipient CD4+ T cells to IL-33 promotes proliferation and inflammatory Th1 immunity, and 4) test if *in vitro* exposure of human islets to IL-33 impairs insulin secretion and decreases islet cell viability in culture.

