#### *Incidence and risk factors for early PTDM*

We prospectively analyzed PTDM incidence (defined as a weekly fasting glucose  $\geq 126$  mg/dL or random glucose  $\geq 200$  mg/dL) during the first 100 days of HCT in 84 patients without diabetes (1). New-onset PTDM was diagnosed in 50 (60%) patients at a median of 23 days after HCT and prior to the start of steroids in the majority. PTDM was associated with inferior survival when analyzed in a time-dependent manner [hazard ratio (HR), 3.27; 95% confidence interval (CI), 1.3-8.2;  $P=0.01$ ]. In multivariate analysis, elevated, pre-transplant fasting C-peptide level independently predicted both new-onset PTDM [odds ratio (OR), 5.9; 95% CI, 1.77-20.22;  $P=0.004$ ] and increased mortality (HR, 1.05; 95%CI, 1.01-1.09;  $P=0.013$ ) (1). This prospective study indicates that compensatory  $\beta$ -cell changes, as evidenced by increased fasting C-peptide level, could be present prior to HCT (and before exposure to immunosuppression) and that changes in glucose metabolism could lead to inferior HCT outcomes.

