### *Hyperglycemic clamp*

After an overnight fast, pre-HCT patients will undergo a hyperglycemic clamp procedure, as described by DeFronzo *et. al.* and by our collaborators (37, 38). Arterialized blood will be collected by using a heating pad after insertion of a venous catheter (39). Baseline values for glucose, insulin, C-peptide, and glucagon will be calculated by averaging the measurements obtained at -20, -10, and -1 minute before initiation of the glucose infusion. At time 0, a 200 mg/kg priming dose of 20% dextrose (Hospira) will be given for 10 minutes. Thereafter, blood glucose will be measured approximately every 5 minutes and plasma glucose will be maintained at 200 mg/dL with a variable infusion of 20% dextrose solution for 150 minutes (37, 38). Insulin, C-peptide, and glucagon will be measured 3 times during the first 10 minutes, and then every 10 minutes from 90 to 120 minutes. At time 120 minutes, 5 gm of the secretagogue L-arginine will be injected over 1 minute while the patient is hyperglycemic (40). Insulin, C-peptide, and glucagon levels will be measured 3 times from time 120-130 minutes and then every 10 minutes from 130 to 150 minutes. At 150 minutes the glucose infusion and the procedure will be stopped.

The clamp, 2 OGTTs, and microdialysis procedure will be repeated after HCT between day+80 to +100 (+/- 10 days). Patients diagnosed with PTDM requiring treatment after HCT will be maintained on short-acting insulin which will be held the morning of the studies. Oral antidiabetes medications are not routinely used at our HCT center, however if prescribed, these agents will be washed out for 5 days prior to the procedure and the patient will be maintained on short-acting insulin as above.

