### *Immune / Metabolic Studies*

In addition to the 6 study visits, this protocol will involve 5 separate blood draws for the patient [pre-transplant, Day +10, Day +20, Day +30, and Day +90 (all +/- 7 days)]. During each blood draw, no more than 50 ml of blood will be drawn for serum and lymphocyte analysis. Aliquots will be analyzed using standard immunologic techniques and by flow cytometry as outlined in the preliminary data section. Blood will be drawn for research purposes at the same time as routine blood sampling. Venous blood will be obtained by accessing the central venous catheter using sterile technique or via peripheral venipuncture. Samples will be coded with a unique alphanumeric identifier at the time of collection so that patient identity will be available only to study investigators and research staff. Codes will be sequential numbers and letters.

Blood samples and database will be maintained indefinitely by the study investigators or the laboratory of [name]/[name] and the research staff. A total of 250 ml of blood will be drawn on 5 occasions for lymphocyte and serum analysis.

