#### *Diagnosis of PTDM*

PTDM is defined by the occurrence of a fasting blood glucose level  $\geq 126$  mg/dL or a random blood glucose level  $\geq 200$  mg/dL at any point from day +1 (day after stem cell infusion) to day +100 after transplant. Fasting blood glucose level will be assessed weekly during routine outpatient visits from day 1 to day 100 after transplant. Patients will be evaluated following an 8 hour overnight fast (water and medications allowed) during standard of care visits. Random blood glucose levels from day +1 to day +100 after transplant will be assessed during standard of care visits or during hospitalization. For hospitalized patients and patients receiving total parenteral nutrition (TPN), all blood glucose determinants will be considered random blood glucose levels for purposes of analysis.

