## 10.2 Statistical Analysis Plan

### *Primary analysis of Subaim 1A*

We will compare pre-transplant insulin secretion (first- and second-phase GSIS) among patients who do or do not go on to develop PTDM. Wilcoxon rank sum test will be applied to compare the population mean difference between these two groups.

Multivariable logistic regression will evaluate whether GSIS is an independent predictor of PTDM after adjusting for the following covariates: gender, conditioning (ablative vs. reduced intensity), or acute GVHD requiring steroids. The estimated OR and 95% CI of the OR will be provided to measure the effect of the association. We will take a similar approach for the primary analysis of Aims 1B and 2 which will compare post-transplant total glucagon secretion during the OGTT ( $AUC_{Glucagon0-120}$ ) and serum IL-33 levels among patients with or without PTDM, respectively.

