### *Secondary analyses for Subaims 1A and 1B*

1) determining if glucagon secretion and OGTT results pre-transplant predict PTDM development (herein OGTT results refers to 2 hour blood glucose and peak/nadir/total hormone levels during OGTT), 2) determining if GLP-1 infusion increases insulin secretion and glucagon suppression compared to OGTT values without GLP-1, 3) comparing GSIS, glucagon suppression, and OGTT results at day +90 among patients with or without established PTDM, and 4) comparing the change in GSIS, glucagon suppression, and OGTT results at baseline to those determined at day +90 after transplant in the entire cohort or among groups stratified based on PTDM, conditioning regimen (ablative vs. reduced intensity) or for the presence or absence of acute GVHD treated with steroids.

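### The Aim 2 secondary analysis tests whether post-transplant IL-33/sST2 predicts PTDM without requiring that the sample precede diagnosis, and the latest samples will mostly follow it

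*Combined protocol and SAP*

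**What the plan says.** The point concerns item 1 under Secondary analyses for Aim 2 in section 10.2: "determining if PTDM is predicted by pre- or post-transplant levels of IL-33/sST2 from serum/tissue microdialysate", or by the frequency of circulating ST2+ Th1 cells and ST2+ Tregs. The item names no draw and no model.

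The timing comes from sections 3.0 and 6.0:

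- **Outcome.** Under Diagnosis of PTDM, a qualifying glucose value counts "at any point from day +1 (day after stem cell infusion) to day +100 after transplant".
- **Earlier cohort.** "New-onset PTDM was diagnosed in 50 (60%) patients at a median of 23 days after HCT" (section 3.0, Incidence and risk factors for early PTDM).
- **Serum and cells.** The Immune / Metabolic Studies section schedules "5 separate blood draws for the patient [pre-transplant, Day +10, Day +20, Day +30, and Day +90 (all +/- 7 days").
- **Microdialysate.** It is collected once before transplant. Then "The clamp, 2 OGTTs, and microdialysis procedure will be repeated after HCT between day+80 to +100 (+/- 10 days"), which is the only post-transplant sample.

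For the islet measures the plan does separate prediction from comparison. Item 1 of the secondary analyses for Subaims 1A and 1B is "determining if glucagon secretion and OGTT results pre-transplant predict PTDM development", so it is confined to pre-transplant values. Item 3 of that list compares day +90 results between patients with and without PTDM that is already established.

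**The concern.** To predict PTDM, a marker has to be measured while the patient is still free of it. The Aim 2 item puts pre-transplant values, early post-transplant draws and samples taken near the end of the outcome window under the same verb. Section 10 contains no landmark, no time-dependent marker model and no exclusion of patients diagnosed before the draw.

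If the text is followed literally, a day +90 sST2 level or a day 80 to 100 microdialysate level can be reported as a predictor of a diagnosis made weeks before. Such a marker may instead reflect PTDM itself or its treatment: patients who need treatment are on short-acting insulin, withheld only on the morning of testing (section 6.0, Hyperglycemic clamp). An odds ratio from these samples cannot show which came first, and the order of events is central to the Aim 2 hypothesis.

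**Working it through.** **The plan's own figure.** Section 10.1, Aim 2: difference 70 pg/mL, SD about 70 pg/mL, so d = 70/70 = 1.0. A two-sided 0.05 t-test needs 16.7, so 17 per group, and power at 17 per group is 0.807. The stated 17 per group reproduces and is not in question. It assumes that every PTDM case contributes.

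**Sampling windows against the outcome window (day +1 to +100).**

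- Microdialysate: 80 - 10 = day 70 to 100 + 10 = day 110. A visit on days 101 to 110 falls after the outcome window has closed.
- Day +90 draw: day 83 to 97, leaving 100 - 97 = 3 to 100 - 83 = 17 days in which PTDM could still occur.
- Day +10, +20 and +30 draws: days 3-17, 13-27 and 23-37.

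**From the median alone.** If the new cohort repeats a median of day 23, at least half of cases are diagnosed by day 23, the earliest date for the day +30 draw. The gap from the median to day 80-100 is (80 - 23)/7 = 8.1 to (100 - 23)/7 = 11.0 weeks.

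**With assumed shapes.** The documents give no onset distribution, so the shapes are assumptions. Each is conditioned on diagnosis by day 100 with median 23: share diagnosed by day t = F(t)/F(100). The shapes are Weibull (0.8, 1.0, 1.5, 2.0), lognormal (sigma 0.5, 0.8, 1.0), and a two-piece uniform with half the cases spread evenly before day 23 and half after.

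Two worked examples at day 80:

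- Exponential (Weibull shape 1.0, scale 36.5): (1 - exp(-80/36.5))/(1 - exp(-100/36.5)) = 0.95.
- Two-piece uniform: 0.5 + 0.5 x (80 - 23)/77 = 0.87. The same formula gives 0.81 at day 70 and 0.94 at day 90.

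Range over all eight shapes, with 17 expected cases:

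| Sample day | Already diagnosed | Cases left of 17 |
|---|---|---|
| 10 | 5-29% | 12-16 |
| 20 | 39-46% | 9-10 |
| 30 | 55-70% | 5-8 |
| 70 (earliest microdialysate) | 81-100% | 0-3 |
| 80 | 87-100% | 0-2 |
| 90 | 94-100% | 0-1 |

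**Sensitivity to the median.** With median day 15, 88-100% are diagnosed by day 80. With median day 40, the figure is 83-95%. In each case the low end is the two-piece uniform: 0.5 + 0.5 x 65/85 = 0.88 and 0.5 + 0.5 x 40/60 = 0.83.

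**Power if only samples before diagnosis count** (d = 1.0, 17 non-cases, two-sided t-test): 9 cases 0.64, 12 cases 0.72, 16 cases 0.79, 17 cases 0.81. A draw on days 3 to 17 comes before the median, so at most 8 of 17 cases can precede it and 9 to 17 remain. With 9 against 17, the difference detectable at 80% power is 1.20 SD, or 1.20 x 70 = 84 pg/mL. With 17 against 17 it is 0.99 SD, or 69 pg/mL.

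**The case against.** The strongest reply is that this is loose wording in a secondary item of an observational study. The item names no model, so it does not commit anyone to using samples taken after diagnosis as predictors. The team's earlier work reports hazard ratios for engraftment sST2 and a time-dependent survival analysis (section 3.0). Specific Aim 2 places the adipose hypothesis before transplant and the systemic one after, so the item could mean pre-transplant tissue and post-transplant serum. That reading is possible, but the literal text is broader and no rule elsewhere narrows it. The gap stands.

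Three stronger readings are tempting, and the documents do not support them.

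- **That the primary analyses of Aims 1B and 2 share the fault.** A reader might infer this because "We will take a similar approach for the primary analysis of Aims 1B and 2 which will compare post-transplant total glucagon secretion" follows "Multivariable logistic regression will evaluate whether GSIS is an independent predictor of PTDM". But the sentence describes a comparison between patients with and without PTDM, and the odds ratio is described as measuring an association. Subaim 1B hypothesises a difference in glucagon levels in PTDM patients, which a concurrent comparison can test. That analysis is valid as written.
- **That post-transplant sampling cannot support prediction, or that the immune timeline in section 2.0 is lost.** The timeline rests on serial draws. Most cases should still be undiagnosed at day +10, and about 54-61% at day +20.
- **That almost every case will certainly precede day 80.** The smooth shapes alone give 93-100%, but the two-piece uniform gives 87%. The day 23 median comes from an earlier cohort of 84, and the documents do not show that it had the same donor restrictions. The word *most* survives; a narrow range does not.

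**Conclusion.** The concern holds for the Aim 2 secondary item. As written, it allows markers measured after diagnosis to be reported as predictors. For day +90 serum and cells and for all post-transplant microdialysate, that would be the usual situation: with a day 23 median, 87-100% of cases are diagnosed by day 80 and 94-100% by day 90. The day +30 draw is also compromised, since at least half of cases are diagnosed by its earliest date. Pre-transplant values are unaffected.

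The percentages rest on the earlier cohort's median carrying over and on assumed onset shapes. The conclusion about the late samples does not depend on day 23 itself, since medians of 15 and 40 days still leave at least 83% diagnosed by day 80. No primary comparison and no sample-size figure is wrong. This is a worthwhile, inexpensive improvement to a secondary analysis.

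**What to change.** In item 1 of the secondary analyses for Aim 2:

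- Limit any claim that IL-33, sST2 or ST2+ cells predict PTDM to samples dated before that patient's diagnosis. Suitable analyses are pre-transplant values, a landmark analysis among patients still PTDM-free on the actual draw date, or a time-dependent Cox model.
- Report day +90 serum and cell results, and all post-transplant microdialysate, as concurrent association. The plan already treats day +90 islet results this way.

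In the primary analysis text, at most add one sentence: odds ratios for post-transplant glucagon, and for IL-33 drawn after diagnosis, are associations and not evidence of an independent predictor. The comparison itself stays as it is.

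All samples are already scheduled and no enrolment figure changes. The cost is precision, because a landmark drops cases diagnosed before the draw. At the day +10 draw, 9 to 17 of 17 cases remain and power for a 1-SD difference is about 0.64 to 0.81, so null results need cautious wording.

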### *General statistical plan*

Data will be presented using means and standard deviations for continuous variables, as well as percentage and frequency for categorical variables. Investigations for outliers and assumptions for statistical analysis, e.g., normality and homoscedasticity will be made for the parametric test such as t-test and mixed model. If necessary, data will be transformed utilizing appropriate transformations such as the log or square root. Comparison between two independent groups, e.g., with or without PTDM, will be carried out using either two-sample t-test or Wilcoxon rank sum test for continuous variables and Chi-square test or Fisher's exact test for categorical variables. A Spearman correlation will be used to test the relationship between 2 continuous variables. For matched analyses and for the comparison of the changes between baseline and day+90 after transplant in the entire cohort, the mean difference will be compared with paired Student's t-test or Wilcoxon signed rank test for continuous

variables and a McNemar's test for categorical variables. To compare the differences between baseline (pre-transplant) and day +90 test results among various groups we will apply linear mixed model to continuous outcomes and generalized linear mixed model to binary/ordinal outcomes. Groups of interest will be created by stratifying patients based on PTDM, conditioning regimen (ablative vs. reduced intensity) or acute GVHD treated with steroids. All data will be stored in a computerized database and analyzed with R version 3.3.1 (R Foundation for Statistical Computing, Vienna, Austria). *P*-values will be 2-tailed and considered significant at *P* <0.05.

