
### *Rationale and clinical application*

HCT recipients are at significant risk for developing new-onset PTDM, which in turn confers inferior survival. The initiating events and mechanisms that culminate in PTDM development remain understudied, and formal recommendations for screening and treatment are lacking. In this proposal, we will use OGTT and hyperglycemic clamps to characterize the onset and role of pancreatic  $\beta$ - and  $\alpha$ -cell dysfunction in metabolic complications after HCT. These results will be adapted into future screening tools for PTDM and translated into therapeutic clinical trials targeting either insulin insufficiency or glucagon excess. By analyzing IL-33 signaling and ST2 expression on Tregs and Th1 cells sequentially before and after transplant, we will 1) investigate the relationship between islet function and ST2 immune regulation during HCT, 2) establish an immune timeline for the development of PTDM, and 3) develop a biological rationale for why treatment/ prevention of metabolic complications could alter ST2 signaling and improve HCT outcomes. We propose that understanding the immunology and the metabolic abnormalities generating PTDM will promote rapid improvements in the care of HCT recipients.

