### *Sources of materials- Patients*

Study participants who have given informed consent will undergo standard of care evaluations or study visits at either the Outpatient Transplant Unit, the inpatient Myelosuppression Unit, or the Clinical Research Center (CRC) at Vanderbilt University Medical Center. Two oral glucose tolerance tests and 1 hyperglycemic clamp will be performed on separate days prior to transplant and then each procedure will be repeated once between day+80 to day+100 (+/- 10 days) after transplant (Figure 5). In addition to the 6 research visits, study blood will be obtained at the following timepoints: pre-transplant (prior to beginning chemotherapy), Day+10, Day+20, Day+30, and Day+90 (all +/- 7 days) (the day of stem cell infusion is considered Day 0). A total of 550 mL of blood will be collected from the patient over approximately 110 days (over 3 to 4 months). Blood will be drawn for research purposes at the same time as routine blood sampling when feasible. Venous blood will be obtained by accessing the central venous catheter using sterile technique or via peripheral venipuncture. Samples will be coded with a unique alphanumeric identifier at the time of collection so that patient identity will be available only to study investigators and research staff. Clinical information, outcomes, and research data will be obtained by patient interview, medical chart review, and from laboratory testing. Information will be stored in a password-protected electronic database.

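### The protocol promises an immune timeline from five draws, but its mixed models cover only baseline versus day +90 and section 10 assigns no analysis to days +10, +20 and +30.

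*Combined protocol and SAP*

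**What the plan says.** Section 2.0, Rationale and clinical application, states the intent: "By analyzing IL-33 signaling and ST2 expression on Tregs and Th1 cells sequentially before and after transplant", the investigators will "establish an immune timeline for the development of PTDM".

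Section 6.0, Immune / Metabolic Studies, says "this protocol will involve 5 separate blood draws for the patient". These are pre-transplant and days +10, +20, +30 and +90, each with a 7-day window either side. Sources of materials- Patients gives the same schedule; Appendix A shows it with the last draw at day 80-100.

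Section 10.2 offers these methods:
- Mixed models: "To compare the differences between baseline (pre-transplant) and day +90 test results among various groups we will apply linear mixed model to continuous outcomes". The generalized linear mixed model for binary and ordinal outcomes is in the same sentence and has the same two time points.
- Paired tests for matched analyses (not further defined) and "for the comparison of the changes between baseline and day+90 after transplant in the entire cohort".
- Two-group comparisons, which "will be carried out using either two-sample t-test or Wilcoxon rank sum test for continuous variables".
- Spearman correlation, and logistic regression for predicting PTDM.

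For Aim 2, the primary analysis compares post-transplant "serum IL-33 levels among patients with or without PTDM, respectively", without naming a draw. The secondary analyses ask whether pre- or post-transplant marker levels predict PTDM and correlate with hormone secretion. They name no draw and no model across draws.

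**The concern.** A timeline is a statement about how a marker moves over several occasions and whether that movement differs between patients who do and do not develop PTDM. The planned models see only the two ends of the schedule. The three draws between them lie nearest to the median onset in the preliminary cohort (day 23; section 3.0, Incidence and risk factors for early PTDM). The protocol's own leads are also early: Th1 cells by day +10 and sST2 at engraftment.

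Two things are at stake. A transient early difference that has gone by day +90 cannot show in a baseline-to-day-+90 comparison. And with no analysis assigned to the early draws, the choice of draw and test for each marker stays open until the data are seen.

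**Working it through.** **Inputs from the documents.** Section 10.1, Aim 2: 17 per group, difference 70 pg/mL, SD about 70 pg/mL, two-sided 0.05, 80% power. Section 6.0: five draws, four of them after transplant.

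**Input assumed.** Within-patient correlation rho between draws. The documents give none, so 0.3, 0.5 and 0.7 are used, equal for every pair of draws, with complete data.

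**1. The plan's figure.** Standardised difference = 70/70 = 1.0. The two-sample t-test needs 16.7, so 17 per group; power at 17 is 80.7%. The stated figure reproduces. It is for one IL-33 value per patient.

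**2. False positives if draws were tested one at a time.** With k independent tests the chance of at least one P<0.05 is 1 - 0.95^k: 18.5% for k = 4 and 22.6% for k = 5. Simulated t-tests on correlated draws (17 v 17, no true difference, 20,000 runs) give:

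| rho | 4 draws | 5 draws |
|---|---|---|
| 0.3 | 17.3% | 20.9% |
| 0.5 | 15.6% | 18.9% |
| 0.7 | 13.0% | 15.0% |

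A Bonferroni split over four draws would cut power for 70 pg/mL at one draw from 80.7% to 61%.

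**3. Group contrast averaged over the four post-transplant draws.** The SD of a patient's mean is the single-draw SD times sqrt((1 + 3 rho)/4). For a 1.0-SD difference held over all four draws:

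| rho | SD factor | Standardised difference | Power | Detectable at 80% power |
|---|---|---|---|---|
| 0.3 | 0.689 | 1/0.689 = 1.45 | 98.4% | 48 pg/mL |
| 0.5 | 0.791 | 1/0.791 = 1.26 | 94.7% | 55 pg/mL |
| 0.7 | 0.880 | 1/0.880 = 1.14 | 89.5% | 61 pg/mL |

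**4. Joint test of group and group-by-time (5 df over five draws).** This was checked at a smaller difference of 0.8 SD, which is not the plan's; there one draw has 62% power. For a steady difference at all five draws, joint power is about 69-77%, 53-61% and 43-50% at rho 0.3, 0.5 and 0.7; the ranges reflect the choice of denominator df. So it beats one draw at 0.3, does no better at 0.5 and is worse at 0.7. For a difference at days +10 to +30 only, joint power is 74-98%.

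**5. Early-only difference under the planned model.** With no difference at baseline or day +90, the group difference in change is zero, so the model rejects at its 5% error rate whatever happens between. The averaged contrast in step 3 is diluted but not blind: a 1.0-SD difference at three of four draws averages 0.75 SD, and dividing by the SD factors gives 1.09, 0.95 and 0.85.

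**The case against.** The strongest reply has four parts.

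- **Per-draw testing is not in the plan.** A reader might infer that days +10, +20 and +30 are to be tested separately. Section 10 says nothing of the kind; it is silent on those draws. This stands, so the rates in step 2 are conditional.
- **The timeline is a goal in the rationale, not a listed outcome.** Aim 2 is worded as before versus after transplant, and its secondary analyses list no comparison of courses. A reader might infer that a stated aim goes untested or that Aim 2 is underpowered. Neither follows: the sized comparison uses one IL-33 value per patient, and its 17 per group reproduces. This limits the weight of the point. It does not remove the gap between five scheduled draws and an analysis of two.
- **A larger model is not always more powerful.** A reader might expect any test over all draws to beat one draw. Step 4 shows otherwise for the joint test when the difference is steady. This stands, and it is why the averaged contrast should lead.
- **PTDM group is defined by events up to day +100.** With median onset near day 23, many later draws follow onset, so group-by-time mixes what precedes PTDM with what follows it. A patient who dies early without PTDM has no complete group label. Both stand; the model must be labelled accordingly.

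**Conclusion.** The gap is real and of moderate weight. The protocol commits to sequential immune measurement and collects five draws. Its longitudinal models use two of them, and the three nearest the expected onset have no assigned analysis. A difference confined to those three draws would not be detected by the planned model.

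Extending the model needs no more patients: at 17 per group and the plan's 1.0-SD difference held over four draws, the averaged contrast has about 90 to 98% power. That rests on equal correlation of 0.3 to 0.7 between draws, a steady difference and complete data. It does not cover the group-by-time test, whose advantage is for differences that change over time. The 13 to 17% (four draws) and 15 to 21% (five draws) false-positive rates apply only if draws are tested one by one without adjustment. No stated number in the plan is wrong on this point.

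**What to change.** In section 10.2, General statistical plan:

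1. Extend the linear mixed model to all five draws for serum IL-33, sST2, ST2+Th1 and ST2+Treg, transformed where needed. Include PTDM group, time as a category, group-by-time and a patient random effect.
2. For each marker, prespecify the 1-df group contrast averaged over days +10, +20, +30 and +90 as the main longitudinal test, and group-by-time as the test of course. Report per-draw differences as estimates with confidence intervals, not as separate tests.
3. State that groups are by eventual PTDM status to day +100, so draws after onset describe course rather than prediction. Add a sensitivity analysis limited to draws before onset, by actual draw date. The day +20 window (days 13 to 27) and the day +30 window (days 23 to 37) both contain day 23, so nominal days will not do.
4. State that use of partial data assumes missing at random and needs a known PTDM status, and say how patients who die or withdraw before that status is settled are handled.

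The cost is SAP wording, slightly more analysis and an explicit missing-at-random assumption. No new samples, visits or patients are needed.
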